To compare patient experience in both arms	
Measure of NRS pain after 30 minutes
 
Measure of satisfaction by Likert Scale (0 to 5)
 
Measure of nausea by Nausea and Vomiting Score (0 to 3)
 
Evaluation of comfort during intervention with the CPOT scale (Critical care Patient Observation Tool 0 to 8) and heart rate
 
Willingness to undergo a potential next labor with VRH
 
Willingness to recommend VRH to acquaintances
										
To assess selected safety and efficacy outcomes in both arms	
Progression of labor
 
Need for epidural
										

	
Need for medication: type and dosages during stay
 
Frequency and type of (severe) adverse events (SAEs) (mother and baby)
 
If the patient removes the headset during the session, motivation is documented.

	
To assess gynecologist and nurse satisfaction
 
Measure of satisfaction of the midwife and obstetrician by the Likert scale (0 to 5)
 
Quality of the therapeutic relationship between the midwife and patient (reported by the midwife in a NRS from 0 to 10)

	
Evaluation of vital signs
 
Oxygen saturation
 
Systolic and diastolic blood pressure
 
Heart rate (during and in between contractions)

NUMBERS OF PARTICIPANTS	38
INCLUSION CRITERIA	
 1. Age: ≥ 18 and ≤ 45 years 2. Pregnant with term gestation 3. Willing to adhere to the rules linked to the use of the VRH headset: turning off mobile phone, visit bathroom in advance, no new visitors and no interference of the partner other than when the woman would ask him so 4. Provision of written informed consent 5. Induced labor
EXCLUSION CRITERIA	
 1. Complicated pregnancy (HELLP,...) 2. Scheduled caesarian delivery 3. Receipt of epidural analgesia or opioid painkillers before start active labor phase 4. Low auditory acuity that precludes use of the device 5. Low visual acuity that precludes use of the device 6. Head or face wounds precluding use of the device 7. Schizophrenia 8. Epilepsy 9. Dizziness 10. Non-proficiency in French and/or Dutch (research language)

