11. STATISTICAL CONSIDERATIONS AND ANALYTIC PLAN

11.1 SAMPLE SIZE

The sample size of the study is computed on the basis of expectations for the the difference of the pain NRS means between the two arms at final analysis. Based on previous studies (Yildrim 2004 and Harmon 1990), we may expect a difference of the pain NRS means of 2 or more between the two arms, with a standard deviation of the pain NRS of 2 in both arms. For a statistical power of 80%, an alpha error of 5% and a two-sided test, 17 evaluable patients are needed in each group to reach statistical significance (calculation performed with Stata/MP 14.1).

Assuming a potential drop out rate of 10% in each arm, a total of 19 patients need to be randomized to each arm. The total number of patients for the study is 38.

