11.4 ANALYSIS

First descriptive analysis will be performed. Qualitative data will be described by frequency and percentage. Quantitative data will be described by mean, standard deviation, median, minimum, and maximum numbers.

Regarding the primary outcome, NRS pain score before and after the intervention will be compared using paired t-test or Mann-Whitney test, depending of data distribution. 95% confidence intervals will be provided.

Regarding secondary outcomes, chi-squared tests will be used to compare frequencies and rates between groups. In case of small cell sizes, we will alternatively use the Fisher's exact test. T-Test or Mann-Whitney test will be used to determine if there is a significant difference between means of the two groups. T-Test or Mann-Whitney test will be also used for all continuous data normally distributed or not such as NRS, Likert scale and physiologic data. Repeated measurements such as Anxiety and Nausea will be handled with appropriate techniques such as paired tests.

Safety variables include the incidence of Serious Adverse Events (SAEs), discomfort and the quality of immediate and distant labor pain analgesia. These data will be tabulated by treatment groups and overall, in contingency table for percentages or in descriptive univariate analyzes for continuous variables.

The Intent-to-Treat (ITT) population will be used for all efficacy and safety analyzes unless otherwise specified. This ITT analysis will include all randomized patients, according to their allocation group.

The Per-Protocol (PP) population will be used to validate the effectiveness of the studied intervention, as specified by the primary outcome. This PP analysis will include all patients in the ITT population who do not have a major violation of the protocol. The list of major violations includes at least:

- Non-administered medication
- Failure to meet an inclusion or exclusion criterion

Patients identified as having major violations will be screened to determine their final exclusion from the PP population, prior to the freezing of the database.

12.QUALITY CONTROL AND QUALITY ASSURANCE

Increased adherence to the protocol is acquired by multiple information sessions about the study for the midwives. Furthermore, a reminder poster will be displayed in their office. Adherence to the protocol by the participants will be monitored daily by a non-blinded investigator (LP) by looking at the daily reports of the study.

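### In the small-cell fallback for binary secondary outcomes, Boschloo's exact test would be a cheap gain over Fisher's; how much depends on a trigger that 11.4 leaves undefined

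*Combined protocol and SAP*

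**What the plan says.** Section 11.4 makes chi-squared the default for comparing frequencies and rates between arms in the secondary outcomes. It then adds: "In case of small cell sizes, we will alternatively use the Fisher's exact test". It gives no threshold and does not say whether observed or expected counts decide. One outcome to which this applies is "Need for epidural", listed in the synopsis.

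The numbers available come from section 11.1: "a total of 19 patients need to be randomized to each arm", and "The total number of patients for the study is 38". That calculation concerns the pain score only. No event rate, target difference or power is given for any binary outcome. The intention-to-treat population in 11.4 is everyone randomized, so the natural base is 19 per arm. If the anticipated drop-outs supply no data, it is 17.

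**The concern.** With two groups this small, Fisher's exact test has a true type I error well below the nominal 5%, because it conditions on the total number of events and few p-values are possible. Another exact test, Boschloo's, uses Fisher's p-value as its statistic and computes its tail probability without that conditioning. It therefore rejects whenever Fisher's test does, and sometimes when Fisher's does not, while its own size stays at or below 5%.

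At stake is some power for binary outcomes that already carry little information in 38 women. No false-positive problem arises from Fisher's test.

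**Working it through.** **1. The plan's own figure.** Section 11.1 assumes a "difference of the pain NRS means of 2 or more between the two arms". Its assumed SD is 2 points per arm. The noncentral t distribution gives 78.1% power at 16 per arm and 80.7% at 17, so 17 evaluable per arm reproduces. Allowing for 10% drop-out, 17 / 0.90 = 18.9, rounded up to 19, and 2 x 19 = 38. There is no corresponding figure for binary outcomes to reproduce.

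**2. Method.** All 20 x 20 = 400 possible results at 19 per arm were enumerated, at two-sided alpha 0.05. Size and power are sums of binomial probabilities over the rejected tables. Boschloo's p-value is the maximum, over the common event rate, of P(Fisher p <= observed Fisher p). Chi-squared is uncorrected. The plan's rule was read in two ways:
- Expected count below 5: with equal arms the smallest expected count is (total events)/2 or (total non-events)/2, so Fisher's test applies at 9 or fewer events or non-events.
- Any observed cell below 5.

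**3. True size at 19 per arm (%).**

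| Common rate | Fisher on all tables | Boschloo on all tables | Plan, expected < 5 | Plan, observed < 5 |
|---|---|---|---|---|
| 10% | 1.05 | 1.46 | 1.06 | 1.05 |
| 20% | 2.16 | 4.20 | 2.95 | 2.16 |
| 30% | 2.38 | 4.35 | 4.95 | 2.70 |
| 40% | 2.79 | 3.74 | 5.72 | 4.11 |
| 50% | 2.82 | 3.51 | 5.31 | 4.64 |

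Over all rates the maxima are 2.8% for Fisher, 4.5% for Boschloo and 5.8% for chi-squared. No table is rejected by Fisher's test and not by Boschloo's.

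**4. Which tables change.** Under the expected-count reading only one pattern and its mirror change: 1/19 v 6/19 and 13/19 v 18/19. For 1 v 6, Fisher p = 2 x [C(19,7) + 19 x C(19,6)] / C(38,7) = 2 x (50,388 + 515,508) / 12,620,256 = 0.090. Boschloo p is 0.045.

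Under the observed-cell reading, 2 v 8 (Fisher 0.062, Boschloo 0.034), 3 v 9 (0.079, 0.040) and their mirrors change too. In 2 v 8 the smallest expected count is (2 + 8)/2 = 5 and in 3 v 9 it is 6. On the expected-count reading chi-squared is used there, and it already rejects (p about 0.027 and 0.036).

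**5. Power gained in the fallback, 19 per arm.** The event rates are assumptions. On the expected-count reading the gain is in effect the probability of 1 v 6, P(1 of 19) x P(6 of 19), the other orderings being negligible:
- 5% v 30%: 0.3774 x 0.1916 = 0.072
- 5% v 35%: 0.3774 x 0.1844 = 0.070
- 10% v 37%: 0.2852 x 0.1714 = 0.049
- 10% v 40%: 0.2852 x 0.1451 = 0.041

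| Rates | Plan's power, expected < 5 | Gain (points) | Plan's power, observed < 5 | Gain (points) |
|---|---|---|---|---|
| 5% v 30% | 43.4% | 7.2 | 41.4% | 9.3 |
| 5% v 35% | 58.7% | 7.0 | 55.5% | 10.1 |
| 10% v 37% | 45.8% | 4.9 | 38.4% | 11.7 |
| 10% v 40% | 54.6% | 4.1 | 46.1% | 11.9 |

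**6. At 17 per arm.** On the expected-count reading no small-cell table changes, so the gain is zero. On the observed-cell reading the gain runs from about 1 point (5% v 30%, 34.7% to 35.8%) to about 7 (10% v 40%, 39.2% to 45.8%).

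**7. Boschloo for every 2x2 table, 19 per arm.** Against the plan on the expected-count reading, power falls from 71.6% to 66.3% at 30% v 70% (5.3 points) and from 75.6% to 69.4% at 40% v 80% (6.2 points). Part of that difference is chi-squared exceeding 5%.

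**The case against.** Fisher's test controls type I error and is the conventional fallback. A size below 5% is not an error, and preferring another exact test is a matter of efficiency. That stands in full.

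A reader might infer from the Fisher column that the plan tests its binary outcomes at 1% to 3% and gives up 9 to 12 points of power throughout. The documents do not support this, because chi-squared is the default. On the expected-count reading Fisher's test is used in about 51% of trials at 10% v 40%, and in about 0.2% when both rates are 50%. The rule's size then rises to 5.7%, and the gain is 4 to 7 points. The larger loss needs the observed-cell reading, under which Fisher's test is used in 97% or more of trials at the assumed rates. Section 11.4 supports neither reading over the other.

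Nor do the documents show that epidural use will be sparse. No rate is given, and section 8 says an epidural is available on request unless contraindicated. At 5% v 20%, even Fisher's test used on every table loses only 3.9 points against Boschloo's (15.0% v 18.9%).

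It is also true that the substitution does not bring the whole rule under 5%. Boschloo's limit holds for that test used on all tables. Where chi-squared still handles the other tables, its excess remains, up to 5.8%.

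**Conclusion.** The point holds as a cheap improvement to one sentence. Within the small-cell fallback, Boschloo's test does at least as well as Fisher's on every table. At 19 per arm the gain is about 4 to 7 points if small refers to expected counts below 5, and about 9 to 12 if it refers to any observed cell below 5. At 17 per arm it is nil and about 1 to 7 points respectively.

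These figures rest on assumed event rates in the sparse range, on two-sided 5% testing (stated in 11.1 for the pain score only), and on uncorrected chi-squared as the default. Only secondary binary outcomes with no stated power are concerned. The primary pain comparison and the sample size are untouched.

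**What to change.** In 11.4, name Boschloo's exact test in place of Fisher's for 2x2 tables with small cells. Say in the same sentence what makes a cell small and whether observed or expected counts decide. Report the risk difference with a 95% confidence interval (for example Newcombe's) for each binary outcome; at present 11.4 promises intervals only in its primary-outcome paragraph.

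The cost is a sentence, a less familiar test name, and software that offers the test, such as R or Python. Patients, data collection and sample size are not affected.

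Using Boschloo's test for all 2x2 tables is an option, but a trade-off. It removes the switch and the chi-squared size of up to 5.8%, at the price of about 5 to 6 points of power at middling rates against the expected-count version of the plan's rule.

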OBJECTIVES AND ENDPOINTS	
 
 Primary objective	Primary endpoints	
 
 To evaluate efficacy of VRH AQUA[©] module on labor-related pain	Difference in NRS (Numerical Rating Scale 0 to 10) pain scores before and after the intervention	
 
 Secondary objectives	Secondary endpoints	
 
 To compare patient experience in both arms	 
Measure of NRS pain after 30 minutes
 
Measure of satisfaction by Likert Scale (0 to 5)
 
Measure of nausea by Nausea and Vomiting Score (0 to 3)
 
Evaluation of comfort during intervention with the CPOT scale (Critical care Patient Observation Tool 0 to 8) and heart rate
 
Willingness to undergo a potential next labor with VRH
 
Willingness to recommend VRH to acquaintances
 	
 
 To assess selected safety and efficacy outcomes in both arms	 
Progression of labor
 
Need for epidural
 	
 
	Primary objective	Primary endpoints	To evaluate efficacy of VRH AQUA [©] module on labor-related pain	Difference in NRS (Numerical Rating Scale 0 to 10) pain scores before and after the intervention	Secondary objectives	Secondary endpoints	To compare patient experience in both arms	
Measure of NRS pain after 30 minutes
 
Measure of satisfaction by Likert Scale (0 to 5)
 
Measure of nausea by Nausea and Vomiting Score (0 to 3)
 
Evaluation of comfort during intervention with the CPOT scale (Critical care Patient Observation Tool 0 to 8) and heart rate
 
Willingness to undergo a potential next labor with VRH
 
Willingness to recommend VRH to acquaintances
	To assess selected safety and efficacy outcomes in both arms	
Progression of labor
 
Need for epidural

Primary objective	Primary endpoints										
To evaluate efficacy of VRH AQUA [©] module on labor-related pain	Difference in NRS (Numerical Rating Scale 0 to 10) pain scores before and after the intervention										
Secondary objectives	Secondary endpoints										

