5.2 SECONDARY OUTCOMES

30 min after the end of the intervention the NRS pain is assessed once more. (T4)

During the intervention the comfort of the patient is evaluated. (T2) To do this we use the CPOT (Critical care Pain Observation Tool). CPOT is a comfort scale for (non)-ventilated patients in the intensive care unit. We decided to use this score, because during the VR experience we cannot communicate with the patient, which is similar as in sedated patients. And in our own experience we see that the parameters that we look at to evaluate the comfort of the patient during a VR sedation are very similar to this scale. (Facial expression, body movements, muscle tension and vocalization together make a score of 0 to 8)^{xvii} Vital signs like heart rate and blood pressure are parameters that are easily measured during the intervention and considered as objective for evaluating pain during labor. (T1,2,3,4) ^{xviii}

Nausea is also actively evaluated. Therefore we use the PONV rating scale from 0 to 3. (T1, T3, T4) Anxiety is evaluated with the NRS at the same time. (T1, T2, T3) We use the Likert satisfaction scale (from 0 to 5) to explore the satisfaction directly after their experience and the day after delivery. (T3, T6)

Willingness to repeat the intervention and to recommend the intervention can correlate with satisfaction of the overall experience. (T6)

Progression of labor is followed with the degree of the cervix dilatation, therefore we will not perform more cervical examinations than needed but interpret the measurement of the midwives/obstetricians. (T5)

The midwives are asked to evaluate the therapeutic link between themselves and the patient (NRS) after the women return to the maternity ward. (T5)

All the medication received during the stay on the delivery ward, adverse events and interruptions from the intervention is noted. (T3, T5)

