6. STUDY DESIGN

The VRH4L trial is an interventional, randomized, controlled, single-center, parallel group trial. Randomization will be done as a block randomization with a 1:1 allocation^{xix}

Clinique Saint-Jean Brussels (SJ), where the study takes place, is an academic hospital in the center of Brussels with around 2000 deliveries per year.

We create two groups: the VRH group and the control group. During the intervention (T1-3) the VRH-group receives a digital sedation in contrary to the control group who will not use the VRH headset.

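### The between-arm comparisons of T4 pain and vital signs leave out each woman's T1 value; the tests are valid but probably give up precision

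*Combined protocol and SAP*

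**What the plan says.** Section 11.4 gives the method for these outcomes: "T-Test or Mann-Whitney test will be also used for all continuous data normally distributed or not such as NRS, Likert scale and physiologic data". No covariate, analysis of covariance or mixed model is named for any outcome. The next sentence allows paired tests, among other suitable techniques, for repeated measurements, with anxiety and nausea as examples.

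The secondary pain endpoint is the score itself. The Synopsis lists "Measure of NRS pain after 30 minutes", and Section 5.2 says "30 min after the end of the intervention the NRS pain is assessed once more", labelled T4. Only the primary outcome (Section 5.1) is defined as a change, T3 minus T1.

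The T1 values are planned. The Section 9 schedule has NRS pain at T1, T3 and T4, and vital signs at T1 to T4. Section 5.2 gives the same four times for heart rate and blood pressure.

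**The concern.** A woman's pain or blood pressure just before the session probably predicts part of her value 30 minutes after it. A between-arm test that leaves T1 out keeps that predictable part in the error term. With about 17 evaluable women per arm, the interval for the T4 difference is then wider than it needs to be.

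The T4 pain score is the direct patient-reported measure of whether relief lasts beyond the session. The trial was sized for a 2-point difference. If the effect has partly faded by T4, power is well below 80%, and a narrower interval is worth having.

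This point concerns the secondary comparisons only, not the choice of test for T3 minus T1.

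**Working it through.** **Inputs from Section 11.1.** "For a statistical power of 80%, an alpha error of 5% and a two-sided test, 17 evaluable patients are needed in each group"; "we may expect a difference of the pain NRS means of 2 or more between the two arms"; SD 2 in each arm; "Assuming a potential drop out rate of 10% in each arm, a total of 19 patients need to be randomized to each arm". Section 6 gives 1:1 allocation.

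**Assumptions.** The SD of 2 is applied to the T4 score. The T1-T4 correlation r is not in the documents, so a range is shown.

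**The plan's own figure.** For a two-sample t-test with difference 2, SD 2 and two-sided 5% alpha, the noncentral t distribution gives 78.1% power at 16 per arm and 80.7% at 17. So 17 per arm is right. Then 17/0.9 = 18.9, which gives 19 per arm and 38 in total. The stated numbers reproduce, and they rest on an unadjusted comparison of scores.

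**Unadjusted T4 comparison.** Standard error = 2 × √(2/17) = 0.686. With 32 degrees of freedom, t = 2.037, so the 95% CI half-width is 2.037 × 0.686 = 1.40.

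**Adjusted for T1.** The residual SD is 2 × √(1 − r²). One further degree of freedom is spent, leaving 31 (t = 2.0395). Chance imbalance in T1 multiplies the variance on average by 1 + 1/(34 − 4) = 1.033. At r = 0.5 the standard error is 2 × √0.75 × √(2/17) × √1.033 = 0.604, and the half-width is 2.0395 × 0.604 = 1.23.

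| r | variance ratio, (1 − r²) × 1.033 | half-width | power, difference 2 | power, difference 1.5 (assumed) |
|---|---|---|---|---|
| unadjusted | 1 | 1.40 | 80.7% | 56.4% |
| 0 | 1.033 | 1.42 | 79.3% | 54.9% |
| 0.2 | 0.992 | 1.39 | 80.9% | 56.6% |
| 0.3 | 0.940 | 1.36 | 83.0% | 58.9% |
| 0.5 | 0.775 | 1.23 | 89.4% | 67.2% |
| 0.7 | 0.527 | 1.02 | 97.3% | 83.1% |

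A simulation of 10,000 trials per value of r at difference 2 agrees. For example, at r = 0.5 it gives 80.4% unadjusted and 89.5% adjusted.

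**Break-even.** Adjustment starts to help at r of about 0.19. At r = 0 it costs 80.7 − 79.3 = 1.4 points of power.

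**Equivalent patients at r = 0.5.** 1/0.775 = 1.29, or about 29% more patients.

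**Effect of the entry threshold.** Treatment starts at an NRS of at least 4, which narrows the spread of T1. In an illustrative truncated-normal model (SD 2, mean 5 to 7), an untruncated r of 0.5 falls to 0.36–0.39, and 0.7 falls to 0.55–0.59. At r = 0.36 to 0.39 the variance ratio is 0.90 to 0.88, which is worth 11% to 14% more patients.

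**Change score instead.** The SD of T4 minus T1 is 2 × √(2 − 2r). Power at difference 2 is 66.6% at r = 0.3, and it only equals the raw-score test, 80.7%, at r = 0.5. Using T1 as a covariate is the better choice.

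**The case against.** The strongest reply is that nothing here is wrong. An unadjusted comparison of arms in a randomised trial has the correct type I error, and its standard error already allows for chance differences at T1. That stands. A reader might infer that the planned T4 and vital-sign tests are biased, but the documents do not support that.

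A reader might also take the gain as free and certain. It is neither. It costs one degree of freedom, depends on a correlation that the documents do not give, and vanishes at low r. The entry threshold may lower r. So may epidurals before T4: Section 18's place in the plan is taken by Section 8, which lets any woman without contra-indications have one on request, and Section 9 records epidural at T3 and T4.

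The most substantive reply is that T1 is not a pre-randomisation baseline. Section 10 has women randomised straight after consent at the prenatal visit, and Section 11.3 says the investigators are not blinded. The Synopsis and Section 10 state the active-labor trigger only for the VRH arm. The T1 column in Section 9 refers to a study threshold for active labor, but it is also tied to the start of AQUA, which controls do not have. If T1 were taken at a different point of labor in controls, adjusting for it could itself introduce bias. This stands as a condition on the fix. The primary endpoint already depends on the same T1 value.

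It could be said that the sentence on repeated measurements leaves room for adjustment. Its wording is open, but the technique it names compares times within women. It does not give a between-arm difference adjusted for T1.

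Finally, a reader might treat T4 pain as the only evidence on lasting relief. Need for epidural and medication received also bear on it.

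**Conclusion.** The point holds as a matter of efficiency on secondary outcomes. Section 11.4 assigns T4 pain and vital signs to unadjusted tests although the T1 values are scheduled, and the unadjusted tests remain valid.

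For T4 pain, with 17 per arm and SD 2, the likely benefit runs from small (r = 0.3: 2.3 points of power at difference 2, half-width 1.36 against 1.40) to useful (r = 0.5: 8.7 points, half-width 1.23). The r = 0.7 figures are probably optimistic. The possible loss is about 1.4 points of power at r = 0.

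The size rests on an assumed r and on the plan's SD applying at T4. For vital signs the documents give no SD, effect or correlation, so no gain can be stated. No change is proposed for nausea, because models for a 0–3 score would be fragile with about 34 women.

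**What to change.** In Section 11.4, before any data are seen:

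- Prespecify a linear model of NRS pain at T4 on arm, with NRS pain at T1 as covariate. Report the adjusted between-arm difference with its 95% CI.
- Do the same for each vital sign at T2, T3 and T4, with its own T1 value as covariate.
- Keep the unadjusted t-test or Mann-Whitney test as a sensitivity analysis.
- State in Sections 9 and 10 that T1 is recorded at the same labor threshold in both arms, and before the session starts in the VRH arm.

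The cost is protocol wording, a few lines of code and one degree of freedom per model. No extra patients or measurements beyond the schedule are needed, but control-arm staff must know when T1 is due.

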10. SELECTION AND WITHDRAWAL OF SUBJECTS

During the prenatal visit (PNV = T0; some weeks before the due date) the pregnant women receive information about the the study and the use of VRH from the midwife. Each patient will be asked for participation in the study, after verifying the presence of the inclusion criteria and absence of any exclusion criteria. The registration checklist is filled in (questionnaire 1). If patients refuse, their motivation will be noted on the refusal questionnaire(questionnaire 4). All the included patients receive sufficient information and time to decide if they want to participate or not. After signing the informed consent (Questionnaire 2 resp) they will be immediately randomized using block randomization (with excel). This will assign the pregnant woman to either control group or the VRH group.

On the day of delivery every included patient will receive standard of care. When the women selected in the VR group are in active labor (NRS pain ≥ 4 , cervical dilatation ≥ 4 cm and regular contractions (every five minutes) we present the VRH treatment (T1).

Patients who refuse the VRH treatment (T1) or remove the VRH headset during(T2) will be asked to fill in questionnaire 4 (refusal questionnaire). They will be considered as drop outs.

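### Safety is analysed by allocation only, so VRH-arm women who never wear the headset modestly dilute device-related adverse-event rates

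*Combined protocol and SAP*

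**What the plan says.** Section 11.4 sets the rule: the ITT population "will be used for all efficacy and safety analyzes" unless otherwise specified. It then defines the set: "This ITT analysis will include all randomized patients, according to their allocation group". The only other analysis set is per-protocol, and its purpose is limited to effectiveness: "The Per-Protocol (PP) population will be used to validate the effectiveness of the studied intervention, as specified by the primary outcome". No safety or as-treated set appears anywhere in the document.

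The same section lists what counts as safety: "Safety variables include the incidence of Serious Adverse Events (SAEs), discomfort and the quality of immediate and distant labor pain analgesia". These data are to be tabulated by group and overall. No safety threshold or formal safety test is given.

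Section 10 fixes the timing. After consent at the prenatal visit, some weeks before the due date, "they will be immediately randomized using block randomization (with excel"). The headset comes much later: only when a woman in the VRH group meets the pain, dilatation and contraction criteria on the day of delivery do the investigators act, in the words "we present the VRH treatment (T1"). Section 11.3 gives every participant a further chance to leave the study on arrival at the labour ward. Section 10 adds that "Patients who refuse the VRH treatment (T1) or remove the VRH headset" during the session complete the refusal questionnaire and are counted as drop-outs.

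**The concern.** Allocation and exposure are separated by weeks, and the plan itself foresees two ways in which a woman can be allocated to VRH and never put the headset on: she drops out on arrival, or she refuses at T1. A third is possible. An epidural or opioid before active labour is an exclusion (section 7.2), but it can only be settled after randomisation has taken place. None of these women can have an event caused by the device, yet the stated rule keeps them in the VRH denominator.

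In a superiority comparison of efficacy, this kind of dilution usually works against the new treatment and is accepted as cautious. For harm it works in the other direction and makes the device look safer than it is. That matters here because section 4.1 says the trial was organised to measure side effects as well as benefits of a technique not previously studied for labour pain, and the synopsis lists adverse-event frequency as an endpoint.

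**Working it through.** **Inputs from the documents.** Section 11.1: difference in means 2, SD 2, power 80%, two-sided alpha 5%, 17 evaluable per arm, 10% drop-out, 19 randomised per arm, 38 in total. Section 11.4: safety denominator is all randomised women, by allocation.

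**The plan's own figures.** A two-sample t-test with a standardised difference of 2/2 = 1 needs 16.71 women per arm, so 17, with power 80.7% at that size. Allowing for drop-out, 17/0.90 = 18.9, so 19 per arm and 38 in total. The stated sample size reproduces.

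**Dilution formula.** Let u be the number of the 19 VRH-arm women who never wear the headset, p1 the event rate in exposed women, and p0 the rate in unexposed women. Then

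ITT rate = [p1 × (19 − u) + p0 × u] / 19.

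For events that occur only with the device, p0 = 0 and the ITT rate is p1 × (19 − u)/19.

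**At the planned drop-out.** The allowance is 19 − 17 = 2 women per arm. If both never wear the headset, u = 2, the factor is 17/19 = 0.895, and a true 20% shows as 0.20 × 17/19 = 17.9%. The difference is 2.1 percentage points, or 0.4 of an event in 19 women.

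**What makes it smaller.**
- Section 10 puts refusers and women who remove the headset under one drop-out label. Removers are exposed. If one of the two drop-outs is a remover, u = 1 and 20% shows as 0.20 × 18/19 = 18.9%.
- Obstetric and neonatal events also occur without the headset. With u = 2 and an assumed background rate of 10%, the ITT rate is (0.20 × 17 + 0.10 × 2)/19 = 18.9%. The excess over background still shrinks by 17/19, from 10.0 to 8.9 percentage points.

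**What would make it larger (assumptions only; the documents give no count of never-exposed women).** With p0 = 0:

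| u | Exposed | Factor | A true 20% shows as |
|---|---|---|---|
| 1 | 18 | 0.947 | 18.9% |
| 2 | 17 | 0.895 | 17.9% |
| 4 | 15 | 0.789 | 15.8% |
| 6 | 13 | 0.684 | 13.7% |

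**If no event is seen.** The one-sided 95% upper bound is 1 − 0.05^(1/n): 14.6% for n = 19 and 16.2% for n = 17. Using the allocated number slightly overstates how much harm has been ruled out.

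**The case against.** The strongest reply is that the effect is lost in the noise. At the planned drop-out the shift is under half an event, while the exact 95% interval for 4 events in 19 women runs from 6% to 46%. Safety is descriptive, so there is no test or margin for dilution to distort. Safety tables by allocation are a legitimate choice and keep the randomised comparison. The exposed number can also be recovered, because the schedule in section 9 records a stopped session and the refusal questionnaire records who declined. All of this stands, and it limits the point to a reporting improvement.

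It can also be said that the handling of drop-outs is unsettled. Section 11.1 sizes the trial as if they were not evaluable, and section 9 schedules adverse events only from T1 to T5, so a woman who never reaches T1 may have missing safety data rather than a zero. That is fair. It does not remove the problem, because section 11.4 still counts her, and it is a reason to reconcile these sections.

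An as-treated comparison also has a cost of its own. If the comparator were everyone who reached T1 without the headset, VRH-arm refusers would be mixed with controls. The comparator should therefore be control-arm women only.

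A reader might infer that device event rates will be understated by about a third. That needs 6 of 19 women never exposed, over three times the planned drop-out, and nothing in the documents supports it. A reader might also infer that every adverse-event rate falls by 17/19. That holds only for events that cannot happen without the device.

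**Conclusion.** The point holds as a modest one. As written, section 11.4 keeps VRH-arm women who were never exposed in the safety denominator, and the direction of the bias is towards zero for device-related events. At the planned 10% drop-out the understatement is at most a factor of 17/19, about 10.5% in relative terms. That bound rests on two assumptions, that both drop-outs never wore the headset and that the event cannot occur without it; relaxing either one brings the figure closer to the truth. It also takes the planned drop-out rate as given; if more women never start the session, the dilution grows as tabulated, but the documents provide no basis for any particular higher number. The documents do not support a claim that the safety reporting is invalid or that a safety conclusion would be reversed.

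**What to change.** In section 11.4:

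- Keep ITT for efficacy.
- Define a safety set by treatment received: all women who started the AQUA session, for any duration and including those who removed the headset, compared with control-arm women who reached the T1 threshold.
- List VRH-arm women who never started the session separately, with their reason and any adverse event.
- Keep the ITT safety table alongside, so that no serious adverse event is lost.

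In section 10, reconcile the drop-out label with the ITT rule: distinguish women who never started from those who stopped early, and say whether adverse events are still collected from both.

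The cost is a few sentences and one extra table. Little or no new data collection is needed, since session stops and refusals are already recorded. The downside is that the safety-set comparison is not strictly randomised, which is why the ITT table should stay.
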